**3.a. Anticipated Adverse Events:**

**3.a.1. Saracatinib-induced side effects:** Studies to date suggest relatively few adverse events of Saracatinib and that it is safe and well tolerated across doses. Diarrhea, headache, fatigue and nausea were the top adverse events observed at 100 and 125 mg dose of Saracatinib in Alzheimer's patients, but the incidence rates were low and did not differ from the rates observed with placebo. The 50 mg dose was associated increased headache in one individual.

**3.b.1. Blood Drawing: Possible adverse events include feeling lightheaded, bruising at the withdrawal site, fainting, and pain.**

**4) Identification of who will perform the safety review and with what frequency****4.a. Establishment of a DSMB to perform the safety review**

We will be accessing the Data and Safety Monitoring Board (DSMB) developed for the Center. The DSMB is multi-disciplinary and includes representatives with expertise in the primary components of the proposed trial. The following individuals will be on the DSMB as voting members:

[name], PhD, [name] (Brown)/ VAMC Chmn., DSMB

[name], Director, Decision Sci. Int., Statistician, DSMB

[name], Dir., Dept. Psychiatry Ethics Committee, IRB Rep., DSMB  
 [name], [name], Fairfield Univ. Ethicist, DSMB

This DSMB will follow the operational guidelines outlined in the YCCI plan for DSMB.

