- SAFTEE (Levine and Schooler, 1986): A tool for systematic assessment of adverse effects in clinical trials which includes 1) open-ended questions about any changes in physical or health problems, appearance, or activity level, and 2) yes/no responses to a specific list of symptoms (which correspond to anticipated adverse events associated with Saracatinib). For each symptom reported, the date of onset, severity (minimal, mild, moderate, severe), whether it was drug-related, and action taken, is recorded. The SAFTEE will be administered daily during the outpatient period, on the ADP day and at follow ups, to monitor and document rates of adverse events.
- Yale Craving Scale (YCS; Rojewski et al., under review; [name] et al., in press): The YCS is a five-item measure that employs a generalized Labeled Magnitude Scale (gLMS) to assess the intensity of craving for alcohol relative to the intensity of the strongest imaginable sensation. A psychometric evaluation of the YCS suggests that it evidenced: 1) good internal consistency, 2) scalar measurement invariance which makes it well suited for between group

comparisons, and 3) concurrent relationships with drinking outcomes. The training exercise and the full 5-item YCS will be administered at baseline. During the ADP, the first item ("desire to drink right now") will be used at each time point. To confirm that use of the single item scale was psychometrically justifiable, we conducted a series of bivariate correlations (using data from 111 participants in earlier CTNA trials) between the YCS item assessing current alcohol craving, the total YCS score, and the Alcohol Urge Questionnaire (Bohn et al., 1995). The YCS single item on current craving correlated strongly with the YCS total score ( $r=0.78$ ,  $p<0.001$ ) and the AUQ ( $r=0.59$ ,  $p<0.001$ ). The YCS had superior psychometric properties relative to the AUQ in measuring craving in dependent and non-dependent drinkers.

- Biphasic Alcohol Effects Scale (BAES; Martin et al., 1993): This scale is used to measure the stimulant and sedative effects of alcohol and has been found to be sensitive to memantine and naltrexone's effects ([name] et al., in press; Kranzler et al., 2000; Swift et al., 1994). We and others have validated the use of a shorter 6-item BAES (Rueger and King, 2013; [name] et al., in press), which will be used.

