The dose proposed in this study, 125 mg, has generally been well tolerated in both healthy volunteers, and in patients with advanced solid tumors. The most common adverse events at this dose have included rash, headache, and diarrhea. Less common adverse events have included nausea, vomiting, anorexia, palpitations, fatigue, influenza-like symptoms, and

abnormal liver function tests. Other adverse effects at higher doses have included upper respiratory infection, myalgia, abdominal pain and tenderness, and epididymitis.

Importantly, with AZD0530 monotherapy, febrile neutropenia or other serious hematologic adverse events have not been documented in doses equal to or lower than 175 mg. In a total of 7 phase 1 trials, including 187 healthy volunteers, no major safety issues were identified from adverse events in any of the doses studied, up to 250 mg daily (AZ Investigator's Brochure). There is a potential for a mild decrease in values for both white cell count and platelets with doses of 125 mg and above, but these abnormalities never fell below reference levels, and levels normalized while patients remained on (AZ Investigator's Brochure). The timing for hematologic effects of AZD0530 is within 14 days of drug initiation, providing the rationale for the 30-day monitoring period in the phase 1 study (AZ Investigator's Brochure). It should be noted that 2/3 of the safety data have been generated from patients with solid tumors, and some of these patients were included in the study despite mild baseline pancytopenia.

In studies where AZD0530 was used to treat patients with cancer the following side effects were noted: GI disorders: nausea, vomiting, diarrhea, decrease appetite, General disorders: flu-like syndromes, asthenia, Hematologic disorders: neutropenia, lymphopenia, thrombocytopenia, leukopenia, anemia, bleeding, bruising, Investigations: increases in serum, creatinine, positive findings on urine dipstick testing for protein and/or blood, elevations in serum transaminases, Respiratory Disorders: pneumonitis, Skin and Sub-cutaneous tissue: rash (general popular).

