**3) Plans for reporting non-serious anticipated and unanticipated adverse events**

The number of subjects (and percentage) reporting each anticipated adverse event would be reported on an annual basis to the IRB, MAC, and NIAAA as part of annual progress report (NIAAA) and annual reapproval (IRB). These will be reported for the overall sample and not by treatment condition in order to maintain the blind. However, if anticipated adverse events occur in greater magnitude or frequency than expected, then these will be reported to the IRB and NIAAA.

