treatment on alcohol craving in response to the alcohol cue exposure just prior to the start of the drinking session using a similar model. In the above models, treatment will be considered as a categorical predictor but linear and quadratic effects of dose will also be tested. **Aim 2:** Total number of drinks consumed during the ADP will be compared among treatment conditions using linear mixed models as above with treatment (0 mg or 125 mg Saracatinib) as a between-subjects factor and session (baseline, post-treatment) as a within-subject explanatory factor. We anticipate a significant treatment by session interaction owing to reduced drinking following Saracatinib treatment, but not placebo. We will also consider change from baseline as the outcome measure and compare the treatment groups using ANOVA.

**Secondary Aim 1:** Alcohol-induced stimulation and sedation during ADP will be evaluated using the same linear mixed models outlined in Specific Aim 1, with BAES subscale scores as the dependent variables.

**Secondary Aim 2:** Adverse events will be recorded and summarized qualitatively by treatment group. Total and severe adverse event frequencies will be compared between groups using chisquare or Fisher's exact test. Similar to what our collaborators, Drs. [name] and [name] observed among AD subjects (see preliminary data), we anticipate AE profiles of the two active Saracatinib groups will be similar to placebo. Vital signs and blood alcohol levels and plasma Saracatinib levels assessed during the ADP will also be evaluated using linear models to examine alcohol-Saracatinib interactions.

**Exploratory Aims:** All measures (e.g., PST, Habit, genetic markers, neural markers) will be evaluated using the same models outlined in Specific Aim 2.

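### The anticipated-event list names 4 of the 10 events reported at 125 mg, so the rest fall outside the non-serious reporting rule and may go unprompted

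*Combined protocol and SAP*

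**What the plan says.** Section V.10 (Data and Safety Monitoring Plan), item 3.a.1, is the only place that lists anticipated drug events. It states that "Diarrhea, headache, fatigue and nausea were the top adverse events observed at 100 and 125 mg dose of Saracatinib in Alzheimer's patients", and continues "but the incidence rates were low and did not differ from the rates observed with placebo". Bruising appears separately, as an effect of blood drawing.

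Two other parts of the plan use the category of anticipated events:

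- The SAFTEE entry under Assessments describes open-ended questions plus "yes/no responses to a specific list of symptoms (which correspond to anticipated adverse events associated with Saracatinib"). Section V.10, item 1, says the same. Neither gives the items.
- Section V.10, item 3, says "The number of subjects (and percentage) reporting each anticipated adverse event would be reported on an annual basis", for the whole sample and not by arm. It adds that anticipated events exceeding the expected magnitude or frequency go to the IRB and NIAAA. Its heading also covers unanticipated non-serious events, but its text gives no rule for them.

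Section V.8 describes 125 mg more fully. "The most common adverse events at this dose have included rash, headache, and diarrhea"; seven less common events follow. It adds: "There is a potential for a mild decrease in values for both white cell count and platelets with doses of 125 mg and above". The healthy-volunteer data there report neutrophil and platelet falls at 125 mg and bleeding events by arm.

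For tolerability (Section V.11, Secondary Aim 2), events are to be summarised qualitatively by group, and "Total and severe adverse event frequencies will be compared between groups using chisquare or Fisher's exact test". The stated expectation is that "we anticipate AE profiles of the two active Saracatinib groups will be similar to placebo"; only one active dose is now planned.

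**The concern.** The anticipated list decides which non-serious events are counted each year, which can trigger an early report and, by the plan's own description, which symptoms the SAFTEE asks about directly. A list drawn from one trial in Alzheimer's patients, and shorter than the plan's own account of the dose, weakens all three.

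The plan treats some of the missing effects as real risks. The exclusion criteria cover anemia, neutropenia, thrombocytopenia, GI bleeding, clotting disorders and warfarin use. At stake is whether an excess of rash, bleeding or liver-test changes would be noticed and reported during the trial, and whether Secondary Aim 2 could describe it afterwards. This is an unapproved drug given with alcohol to heavy drinkers.

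There is a related gap in analysis. Blood counts and liver and kidney tests are repeated on the morning after the second drinking session and at one week. Secondary Aim 2 plans models for vital signs, blood alcohol and plasma drug levels, but does not mention these safety tests.

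**Working it through.** The plan states no figure to reproduce on this point. The check is a comparison of lists, followed by an illustration of size.

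**1. Lists side by side**

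| Event at 125 mg (Section V.8) | In the anticipated list (V.10, 3.a.1)? |
|---|---|
| Rash (most common) | No |
| Headache (most common) | Yes |
| Diarrhea (most common) | Yes |
| Nausea | Yes |
| Vomiting | No |
| Anorexia | No |
| Palpitations | No |
| Fatigue | Yes |
| Influenza-like symptoms | No |
| Abnormal liver function tests | No |

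Total 3 + 7 = 10; listed 4; missing 6, including 1 of the 3 most common. White-cell, neutrophil and platelet falls and bleeding are outside the ten and also missing, so ten is not an upper limit.

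**2. Reporting rule**

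Item 3 of the monitoring plan counts anticipated events and applies its trigger to them. A non-serious rash, nosebleed or liver-test rise is on neither route. This follows from the text and does not depend on the SAFTEE form. Serious events have their own 24-hour rule and are unaffected.

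**3. The only missing effect with rates by arm**

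Bleeding in healthy volunteers (Section V.8):

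- Drug 33/187 = 17.6%; placebo 6/57 = 10.5%; difference 7.1 points. Newcombe 95% CI -4.5 to 15.4; Fisher p = 0.22.
- Expected numbers in this trial: 40 × 0.1765 = 7.1 v 20 × 0.1053 = 2.1.

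**4. What under-capture would do**

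Let *d* be the share of events that open questions catch relative to a yes/no item, equal in both arms. The documents give no value; 0.25 to 0.75 is assumed. The observed difference is *d* × 7.1:

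- *d* = 0.25: 1.8 points
- *d* = 0.50: 3.6 points
- *d* = 0.75: 5.3 points
- *d* = 1: 7.1 points, with no loss

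If the total means participants with any event, and other symptoms occur independently in a proportion *b* of both arms (0.3 to 0.6 assumed), the observed difference is (1 − *b*) × *d* × 7.1:

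- *b* = 0.3, *d* = 0.75: 3.7 points
- *b* = 0.6, *d* = 0.25: 0.7 points
- *d* = 1: 5.0 points (*b* = 0.3) or 2.8 points (*b* = 0.6)

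Even with full capture, an any-event total hides most of a single-event difference when background symptoms are common. That supports counts per event whatever the form asks. The documents give no size for rash, liver-test or blood-count effects, so none is computed.

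**The case against.** A reader might infer that the list steers the tolerability comparison towards a finding of no difference from placebo: four events said not to differ are asked about and the rest are not. The documents do not support that, for these reasons:

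- **The form is not available.** The plan does not say that the SAFTEE items are limited to item 3.a.1. They could equally follow Section V.8.
- **Capture is wider than the checklist.** Open questions ask about health and appearance, which could well elicit rash or bruising. Participants attend daily and events are reviewed daily. Liver and blood-count changes are found by laboratory test, whatever the symptom list.
- **The analysis is not restricted.** Total and severe events are not limited to anticipated ones, and a qualitative summary by group is already planned.
- **The list is not shown to be selective.** It includes two of the three most common events.
- **The one measured effect is weak evidence.** The bleeding data pool doses, were mostly epistaxis or venipuncture-site bleeding, and all drug-related events were grade 1. The interval includes zero. At full capture, Fisher power at 40 v 20 is about 7%, so the planned test could say little either way.
- **The net direction is not fixed.** More prompts also raise background reports. Going from *d* = 0.75, *b* = 0.3 (3.7 points) to *d* = 1, *b* = 0.6 (2.8 points) shrinks the any-event difference.

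All of this stands against a claim of bias. It does not answer the mismatch between the lists, the missing reporting rule, or the absence of a stated summary by arm of safety laboratory results. Section V.11 says that all outcomes will be summarised descriptively, but names neither these tests nor the arms.

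**Conclusion.** The concern holds as a mismatch in safety monitoring and a gap in the tolerability analysis. The list covers 4 of 10 events for the study dose and omits bleeding and blood-count falls. Read as written, the plan gives these effects no non-serious reporting rule.

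Under-capture is a further risk, conditional on two things that the documents do not settle: that the SAFTEE items follow item 3.a.1, and that open questions miss some events. If either fails, the symptom comparison is unaffected. For bleeding, the loss would take an observed 7.1 points down to between 1.8 and 5.3 under the assumed capture rates. These figures are illustrative and show neither harm nor bias.

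The blood-count falls described at 125 mg stayed within the reference range, so the case for including them is completeness of monitoring and not a known clinical danger.

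**What to change.** 1. **Section V.10, item 3.a.1.** List as anticipated all ten events from Section V.8, plus bleeding or bruising and falls in white cells, neutrophils and platelets. The existing counting and trigger rule then covers them.
2. **SAFTEE.** State the yes/no items and confirm that they include rash, vomiting, appetite loss, palpitations, flu-like symptoms, and bleeding or bruising. If they already do, only the text changes.
3. **Section V.11, Secondary Aim 2.** Add wording such as: *For each anticipated event, the number of participants per arm and the difference with a 95% confidence interval will be reported. Blood count, liver and kidney results at screening, the morning after the second drinking session and one week will be summarised by arm, descriptively and without significance tests.*

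As a clerical matter, the dose justification places the white-cell and platelet falls above 125 mg, and should be aligned with Section V.8, which includes 125 mg.

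The cost is one longer list, about six yes/no items per SAFTEE and two sentences of analysis text, with no added visit, blood draw or participant. Direct questions will raise reports in both arms, and more rows will bring some chance differences. Intervals will be wide: 7/40 v 2/20 gives a difference of 7.5 points (Newcombe 95% CI -14 to +24). Blood values after the second session also reflect that evening's drinking, which the drug may change, so they should be read with the one-week results.

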**4.b. Frequency of Review of Safety Reports**

Subjects are recruited at a maximum rate of 2 per month; thus, the DSMB will review safety reports two times a year. More frequent meetings will be scheduled if indicated by interim findings.

- d. For multi-site studies for which the Yale PI serves as the lead investigator: N/A
  - i. How will adverse events and unanticipated problems involving risks to subjects or others be reported, reviewed and managed?
  - ii. What provisions are in place for management of interim results? iii. What will the multi-site process be for protocol modifications?

**11. Statistical Considerations:** Describe the statistical analyses that support the study design.

**Power Calculations:** We will recruit up to 90 subjects and randomize 40 subjects to the 125 mg Saracatinib dose and 20 subjects to placebo. We will use the number of drinks consumed at the baseline session (5 or less, 6 or more) and gender as stratification variables in the randomization. 6 drinks is half the total number of drinks they are allowed to drink in the self-administration period and will allow the participant to reach a BAC of 0.07 or higher which is the threshold for heavy drinking. We anticipate that we will obtain complete data on 52 subjects in approximately 2:1 ratio on active vs. placebo. This would give us 80% power to detect large effects of drug ( $d=0.8$  or greater) at two-sided alpha level of 0.05. Such an effect size is considered clinically meaningful and is consistent with our pilot data where we observed large effects of the 125 mg dose (administered over eight days) on alcohol-induced stimulation and feeling intoxicated and feeling good (all  $>0.8$ ) following exposure to a fixed dose of alcohol (0.8 mg/kg) in heavy social drinkers. Randomizing more subjects on active drug will allow us to explore relationships between potential predictors (e.g. gender, smoking status) and outcome in the treatment group. Thus, we will be well powered with our proposed sample to detect clinically relevant effects of Saracatinib.

**Statistical analyses:** All data will be transcribed onto teleforms, checked for completeness and clarity, and sent to the data manager, [name]. All outcomes will be summarized descriptively and assessed for normality prior to analysis using normal probability plots and Kolmogorov test statistics. Transformations or nonparametric analyses will be performed as necessary. In the mixed models described below, the correlation between repeated measures on an individual will be modeled using random effects and/or structured variance-covariance matrices. The best fitting variance-covariance structure will be determined by information criterion. The mixed effects approach is advantageous in that it is unaffected by randomly missing data and allows greater flexibility in modeling the correlation structure of repeated measures data (Gueorguieva & Krystal 2004). All tests will be two-sided and considered statistically significant at  $\alpha=0.05$ . Significance levels for secondary comparisons will be adjusted for multiple tests using the Bonferroni correction, basing the adjustment on the number of conceptually related statistical tests within each hypothesis.

**Aim 1:** Scores on the Yale Craving Scale will represent the dependent variable in a linear mixed model with treatment (0 or 125 mg Saracatinib) as a between-subjects factor and time (see time points, Table 1) and session (baseline, post-treatment) as within-subject factors. All multilevel interactions will be modeled and interpreted by plotting and comparing least squares means. We anticipate a significant treatment by time by session interaction explained by greater posttreatment reductions in craving with Saracatinib compared to placebo. We will also explore the influence of

treatment on alcohol craving in response to the alcohol cue exposure just prior to the start of the drinking session using a similar model. In the above models, treatment will be considered as a categorical predictor but linear and quadratic effects of dose will also be tested. **Aim 2:** Total number of drinks consumed during the ADP will be compared among treatment conditions using linear mixed models as above with treatment (0 mg or 125 mg Saracatinib) as a between-subjects factor and session (baseline, post-treatment) as a within-subject explanatory factor. We anticipate a significant treatment by session interaction owing to reduced drinking following Saracatinib treatment, but not placebo. We will also consider change from baseline as the outcome measure and compare the treatment groups using ANOVA.

**Secondary Aim 1:** Alcohol-induced stimulation and sedation during ADP will be evaluated using the same linear mixed models outlined in Specific Aim 1, with BAES subscale scores as the dependent variables.

**Secondary Aim 2:** Adverse events will be recorded and summarized qualitatively by treatment group. Total and severe adverse event frequencies will be compared between groups using chisquare or Fisher's exact test. Similar to what our collaborators, Drs. [name] and [name] observed among AD subjects (see preliminary data), we anticipate AE profiles of the two active Saracatinib groups will be similar to placebo. Vital signs and blood alcohol levels and plasma Saracatinib levels assessed during the ADP will also be evaluated using linear models to examine alcohol-Saracatinib interactions.

**Exploratory Aims:** All measures (e.g., PST, Habit, genetic markers, neural markers) will be evaluated using the same models outlined in Specific Aim 2.

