## SECTION V: RESEARCH PLAN

1. **Statement of Purpose:** State the scientific aim(s) of the study, or the hypotheses to be tested. Alcoholism is a disorder that is mediated by multiple genes and environmental factors. Existing medications like naltrexone and acamprosate are not efficacious in all drinkers. Therefore, we need to develop new and effective strategies to treat alcoholism. Development of medications for this disorder should be based on our understanding of the behavioral and neurochemical mechanisms mediating alcohol reward and drinking. There is extensive preclinical evidence suggesting that glutamatergic circuits are involved in the acute behavioral effects of alcohol as well as in alcohol tolerance and withdrawal. This project will evaluate the effect of an agent that indirectly modulates NMDA-R signaling without directly antagonizing NMDA-Rs on alcohol drinking. Specifically, we will test the influence of Saracatinib, a Src/Fyn protein tyrosine kinase inhibitor that modulates NMDA-R signaling via Fyn inhibition.

**Primary Aim 1:** To evaluate the effects of Saracatinib (125 mg/day) versus placebo on alcohol craving.

*Primary hypothesis 1a:* Saracatinib (125 mg/day) will reduce craving for alcohol after exposure to the priming drink of alcohol, and during the free-choice drinking period, when compared with placebo.

**Primary Aim 2:** To evaluate the effects Saracatinib (125 mg/day) versus placebo on alcohol drinking

*Primary hypothesis 1b:* Saracatinib (125 mg/day) will reduce number of drinks consumed during the free-choice drinking period, when compared with placebo.

**Secondary Aim 1:** To evaluate the effects of Saracatinib (125 mg/day), versus placebo, on alcohol-induced stimulation and sedation during the ADP.

**Secondary Aim 2:** To examine the tolerability of Saracatinib (125 mg/day) in heavy drinkers.

**Exploratory Aims:** To explore predictors of Saracatinib response. The predictors have been selected based on findings from our earlier work and include behavioral outcomes like impulsivity, habit and deficiency in loss-avoidance learning, genetic markers related to alcohol drinking or glutamate and Src/Fyn systems, and neural networks/markers identified using multimodal neuroimaging.

2. **Background:** Describe the background information that led to the plan for this project. Provide references to support the expectation of obtaining useful scientific data.

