This novel project will conduct the first test of whether human alcohol consumption may be altered by targeting an intracellular signaling protein implicated in alcohol dependence, Fyn kinase.

Alcohol-seeking behaviors involve complex interactions between neurotransmitters like dopamine and opioids that underlie reward in the nucleus accumbens and engage habits in the dorsal striatum, and glutamatergic pathways from the prefrontal cortex and basolateral amygdala to the nucleus accumbens that are involved in the reinstatement of alcohol drinking (e.g. Koob and Volkow, 2010).

Using the alcohol drinking paradigm (ADP) that is being used in the current study, we showed in our earlier studies that naltrexone reduced drinking in FHP heavy drinkers ([name] et al., 2007) but did not reduce alcohol craving. In subsequent studies we observed that a low dose (20 mg) of the NMDA receptor (NMDA-R) antagonist, memantine, reduced alcohol craving, but not drinking ([name] et al., in press). Further, the higher dose of memantine (40 mg) reduced alcohol craving, but increased drinking and alcohol-induced stimulation among those who were more behaviorally impulsive. Therefore, we hypothesized that a more nuanced approach of altering NMDA-R signaling, that reduces alcohol drinking and craving without increasing positive alcohol effects, might be needed. In an ongoing project, we are studying the potential synergy of low dose memantine (which reduced craving) with 50 mg naltrexone (which reduced drinking; HIC protocol 1005006779). In this project, we propose to examine the effects of an agent that indirectly modulates NMDA-R signaling without directly antagonizing NMDA-Rs. Specifically, we will test the influence of Saracatinib on drinking behaviors.

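### Do two primary hypotheses, each tested at two-sided 0.05, need a rule saying whether one or both must succeed?

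*Combined protocol and SAP*

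**What the plan says.** In the combined protocol and SAP, Section V item 1 (Statement of Purpose) sets two primary aims, each with its own hypothesis. Under 1a, saracatinib "will reduce craving for alcohol after exposure to the priming drink of alcohol, and during the free-choice drinking period". Under 1b, it "will reduce number of drinks consumed during the free-choice drinking period, when compared with placebo".

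Section V item 11, Statistical analyses, sets the level: "All tests will be two-sided and considered statistically significant at" 0.05. The next sentence reads "Significance levels for secondary comparisons will be adjusted for multiple tests using the Bonferroni correction", and continues "basing the adjustment on the number of conceptually related statistical tests within each hypothesis". For craving the plan adds "We anticipate a significant treatment by time by session interaction"; for drinks, "We anticipate a significant treatment by session interaction". The Power Calculations paragraph uses one unsplit two-sided 0.05 for d=0.8 and does not name the outcome.

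No section orders the two hypotheses, divides alpha, requires both, or says that either one is enough. No section claims control of error across the pair either.

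**The concern.** Two outcomes labelled primary, both tested at full alpha, with adjustment only for secondary comparisons, is the usual picture of uncontrolled multiplicity. If the trial could be called positive on whichever outcome succeeds, the false-positive rate for that conclusion would exceed 5%.

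A split result is also foreseeable. Section V item 2 (Background) reports that in this same drinking paradigm naltrexone reduced drinking but not craving, while a low dose of "memantine, reduced alcohol craving, but not drinking". The same section then looks for an agent that lowers both. A reader could take that as a both-required criterion, take the two separate aims as two claims, or take the shared numbering (1a, 1b) as two parts of one hypothesis. Error rate and power both depend on which reading applies.

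**Working it through.** **1. The plan's own figure.** Inputs from Power Calculations: 52 completers, about 2:1, d=0.8, two-sided 0.05, stated power 80%. In the normal approximation, power = Φ(d·√(n₁n₂/N) − 1.96).
- Exact 2:1 gives 77.6%.
- For 35:17 (an assumed whole-number split), 0.8·√(35·17/52) = 2.706, so Φ(2.706 − 1.96) = 77.2%. The noncentral t with 50 df gives 75.6%.
- For 34:18 the t-test gives 76.8%. For 26:26 it gives 80.7%, so the stated 80% fits equal allocation.

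That shortfall is a separate matter. Below, 75.6% is only the baseline for comparing rules.

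**2. Error rate under each reading, no true effect.** The documents give no correlation between the two test statistics, so it is varied as an assumption. For independent tests, P(at least one rejection) = 1 − 0.95² = 0.0975. For correlated tests it comes from the bivariate normal with cut-off 1.96. P(both) = 0.10 − P(at least one).

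| Correlation | At least one rejection | Both rejected |
|---|---|---|
| 0 | 0.0975 | 0.0025 |
| 0.3 | 0.0951 | 0.0049 |
| 0.5 | 0.0907 | 0.0093 |
| 0.7 | 0.0835 | 0.0165 |
| 0.9 | 0.0704 | 0.0296 |

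In the beneficial direction only, the either-one figure is 1 − 0.975² = 0.0494 at correlation 0 and 0.0352 at 0.9, against 0.025 for one test. If both are required and one effect is real, a false joint claim still needs rejection of the one true null, so it cannot exceed 0.05. If the hypotheses are separate claims, each has error 0.05. Only the either-one reading inflates anything.

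**3. Which reading the text fits.**
- Section V item 1: one aim, one outcome and one hypothesis each. This points to separate claims.
- Section V item 11, Statistical analyses: a separate model and expected interaction for each aim, and multiplicity counted inside a hypothesis, not across hypotheses. This points to separate claims.
- Power Calculations: alpha not split. This fits separate claims or both-required, not a split for either-one.
- Section V item 2: earlier drugs are described outcome by outcome (separate claims); the wish for an agent that lowers both is motivation, not a success criterion.
- Section V item 2 calls the trial proof-of-concept, and Section VI A item 5 says it is not a treatment trial. There is no single efficacy verdict for either outcome to carry.

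**4. What a stricter rule would cost.** Two t-tests, 35:17, d=0.8 (simulated for the joint figures):

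| Rule | Power |
|---|---|
| Each at 0.05 | 75.6% per endpoint |
| Bonferroni, each at 0.025 | 65.4% per endpoint |
| Holm, both effects real, correlation 0.3 | 71.5% per endpoint |
| Holm, one effect real, correlation 0.3 | 65.7% for that endpoint |
| Both required at 0.05, correlation 0 / 0.3 / 0.9 | 57% / 60% / 70% jointly |

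Holm therefore costs 75.6 − 71.5 = 4.1 points to 75.6 − 65.7 = 9.9 points per endpoint. The effect detectable with 80% power rises from d=0.845 at 0.05 to d=0.935 at 0.025.

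**5. No hidden extra test for drinks.** The plan also mentions an ANOVA on change from baseline. With two sessions and complete data, its t statistic equals the treatment-by-session t statistic (confirmed in three simulated data sets), so it is not a further chance of a false positive.

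**The case for a change.** The strongest case for a change is that silence lets the meaning of a split result be chosen after it is seen. Such a result is not rare. Even with both effects real at d=0.8, exactly one test is significant with probability 2 × (75.6% − 60.2%) = 31% at correlation 0.3, 2 × (75.6% − 57.3%) = 37% at 0, and 2 × (75.6% − 69.9%) = 11% at 0.9. A sentence settling the matter would need no new data.

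What stands is that the rule is unwritten and that the labels 1a and 1b leave some ambiguity. What does not stand is that this makes any planned test wrong. Both outcomes are named in advance, so a split result is reported as one hypothesis supported and the other not, which is how the Background reports naltrexone and memantine. A reader who wants control across the pair can compare the two p-values with 0.025 and 0.05 by Holm.

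A related argument is that the plan only anticipates a three-way term for craving, and that a reduction equal at every time point would leave that term at zero. That concerns the choice of craving test, not the rule across the two hypotheses. The planned model includes the lower-order interactions and compares least squares means, so the treatment-by-session effect is available from it.

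**Conclusion.** The observation is accurate, but no change follows. Inflation to between 7.0% and 9.75% (correlation 0.9 to 0) requires an either-one success rule that the plan does not contain. On the reading the text supports best, two claims each tested at two-sided 0.05 and both reported, each claim has its nominal error rate. The plan promises no control across the pair, so no promise is broken.

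Moving to Holm, or requiring both, is a trade-off on which statisticians would differ. In a proof-of-concept trial with about 52 completers it gives up roughly 4 to 10 power points per endpoint, or leaves about 60% joint power, for a protection the design does not seek.

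The power figures assume d=0.8 on both outcomes, a 35:17 split, a two-group t-test that ignores the baseline session, and an assumed correlation. They rank the rules and do not give the power of the planned mixed models, least of all the three-way craving term. The conclusion would differ only if a single overall verdict were to be drawn from whichever hypothesis succeeded.
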